4.2 Objective Misallocation of Treatment – Alternative Specifications

As auxiliary outcomes, we will run the same treatment misallocation regression as in Section 3.5 separately for each possible test (with only patient fixed effects).

In addition, we will assess the contribution of different types of non-compliance with test results by coding patient-test-note level indicators for

- Misallocation due to overprescription: a condition is treated that the patient is confirmed not to have
- Misallocation due to undertreatment: a condition the patient is confirmed to have is not treated
- Misallocation due to incorrect dosing or drug choice: a condition the patient has is treated but the dosing or medication chosen is inappropriate.

Note that the misallocation indicator in Section 3.5 is the union of all three of these cases. We will test each of these three as dependent variables in the same regression as the misallocation indicator.

4.3 Relationship of QALY Loss to Severity of Patient Condition

In patients with only mild illnesses, the scope for QALY loss from mistakes may be limited relative to patients with more severe illnesses.

To assess this, we will regress QALY loss on indicators for mild, moderate, and severe illnesses (as assessed by the MO) each interacted with the assisted note indicator, controlling for patient fixed effects. We will show the results graphically.

4.4 Medical Testing Decisions

We will assess the potential misallocation of medical testing in two ways. First, we will measure it based on the screening test outcome. For each test type, we will create an indicator that is coded as 1 if the CHEW recommends conducting a test that turns out to be negative, and a second indicator that is 1 if the CHEW neglects to request a test that turns out to be positive.

Second, we will also construct a (patient,test,note) level indicator that measures whether the CHEW and MO requested the same or a comparable medical test (e.g. the CHEW requested a malaria RDT whereas the MO requested a malaria bloodsmear).

Finally, we will combine these indicators and count as a mismatch if and only if either: i) a test was not requested by the CHEW but was positive, or ii) the test was requested by the cCHEW but the result was negative and no equivalent test was ordered by the MO. This accounts for the possibility that good clinicians might sometimes order tests which are more likely to be negative “just in case”.

4.5 Subjective MO Review Outcomes

We will report treatment effects on all MO evaluation measures listed in section 2.3.1.

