2.3.1 The MO's SOAP note evaluation

The evaluation focuses on treatment errors in the SOAP note that could cause some form of (medical) harm to the patient.

For each SOAP note, the MO first takes stock of qualitative differences between the CHEW's and the MO's plan, then assesses the type of harms for the patient from any errors, and finally rates the SOAP note on a scale for “healthy time lost”. The MO is blinded to whether the SOAP note is LLM-assisted or unassisted and rates SOAP Note A before seeing SOAP Note B.

Deviations from the MO's SOAP The MO is asked to assess for each SOAP note whether medical tests ordered were necessary or clinically useful vs. unlikely to be useful, whether there are missing or incorrect/unnecessary diagnoses, and whether there are missing or incorrect/unnecessary treatment plan elements.

Types of harm incurred The MO is asked to assess any short-term harm (additional symptoms or discomfort for some period), and any long-term serious harm (risk of impairment, death etc.) from the treatment plan in the SOAP note.

Measuring Healthy Time Lost in DALY The MO also provides an overall rating that is intended to reflect the “healthy time lost” from any errors in treatment in the SOAP note. For each assessment and plan constructed by a CHEW (with or without LLM advice), an MO will assess the expected magnitude of healthy life that would be lost if the CHEW plan were implemented instead of the MO's plan. Healthy time is measured in units of disability-adjusted life year (DALYs), which reflect both length and quality of life. Losing one DALY is equivalent to losing a year of life in perfect health, or two years of life experienced in an unhealthy state with a utility weight of 0.5, etc.

MOs estimate DALY losses with the aid of a DALY scale. The DALY scale consists of a set of cutoff points that were calibrated using benchmarks of expected DALY loss for clinical mistakes relevant to local medical practice. Because the DALY consequences of permanent harm (death or disability) are higher for children than for adults, and because different clinical mistakes are relevant for children and adults, we provide a separate DALY scale for the evaluation of CHEW notes for patients who are children (under 18) and patients who are adults.

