3.2 Any Treatment Error

During SOAP note evaluation, the MO is asked to indicate whether the treatment plan for the patient contains any error, conditional on the MO’s own diagnosis.

The introductory text (here for SOAP Note A) is:

Treatment in SOAP Note A:

Please evaluate whether the treatment in SOAP Note A is appropriate for this patient’s condition.

Please base this on *your own diagnosis*, not the CHEW’s diagnosis in SOAP Note A.

The treatment includes medications as well as other care instructions, such as information on home care or referrals.

This is followed by the question:

Is the treatment plan for the patient in SOAP Note A completely appropriate given your *own* diagnosis (accounting for conditional treatments based on medical tests)?

Answer “No” if the patient should receive different medical care given your diagnosis. This can include both minor differences (for example, the patient should be advised to rest) and major errors (for example, the patient should receive a completely different set of medications).

(Answer options: yes/no/unsure)

If the answer is yes, the MO is asked to confirm once more. The same question is asked for SOAP Note B. We will code this question as an indicator variable that equals 1 if the treatment in the SOAP note contains an error and 0 otherwise.

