3.4 An indicator for the better treatment plan

Based on the DALY rating of SOAP Note A vs. B (counting instances with no errors as 0 DALY loss) we will define an indicator that is 1 if the SOAP Note has the better treatment plan (lower DALY loss). This indicator is 0 for both notes if the notes are judged to be the same according to this question, asked after the MO rated Note A:

Are there any *meaningful* differences in the treatment plans of SOAP Note A and B?

Only if the answer is “yes” or “unsure”, the review of SOAP Note B proceeds.

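### As worded, the treatment-plan question in SAP 3.4 stops the Note B review, so some pairs would lack the Note B test and diagnosis ratings that 4.5 needs

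*SAP*

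**What the plan says.** SAP 2.3.1 sets out what the MO rates. On tests: "The MO is asked to assess for each SOAP note whether medical tests ordered were necessary or clinically useful vs. unlikely to be useful". On diagnoses: "whether there are missing or incorrect/unnecessary diagnoses". Treatment elements, types of harm and healthy time lost follow.

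SAP 4.5 makes all of these secondary outcomes: "We will report treatment effects on all MO evaluation measures listed in section 2.3.1". The opening of section 4 applies the primary analysis approach unless stated otherwise. That approach is the patient fixed-effect comparison of the two notes in 3.1.

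SAP 3.4 describes a question put to the MO once Note A has been rated: "Are there any *meaningful* differences in the treatment plans of SOAP Note A and B". Only on an answer of yes or unsure, it says, "the review of SOAP Note B proceeds". For pairs judged the same, one coding rule is given, and it concerns the better-plan outcome alone: "This indicator is 0 for both notes if the notes are judged to be the same according to this question".

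SAP 3.2 shows how treatment is explained to the MO: "The treatment includes medications as well as other care instructions, such as information on home care or referrals". Test orders and diagnoses are not named there.

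**The concern.** The question in 3.4 asks about one domain, treatment, but its answer appears to decide whether all domains are rated for Note B. If the LLM leads the CHEW to drop an unhelpful test or correct a diagnosis, and the treatment stays the same in the MO's eyes, the MO can properly answer no. Note B then has no test or diagnosis rating.

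The SAP does not say how such a pair enters the 4.5 analysis, and neither obvious choice estimates the effect of assistance in all patients. Leaving Note B missing removes the pair from a fixed-effect comparison. The removal depends on whether the two treatment plans differ, which is itself a consequence of the LLM feedback. Carrying Note A's rating over records no change where the notes did change. Changes in testing are an effect the authors expect: the CHEW feedback item in 2.4 gives avoidance of an unneeded test as an example of benefit, and 5.3 names undertesting for malaria as a discrepancy to follow over time.

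**Working it through.** The SAP gives no figure for this point, so there is none to reproduce. The check is a side-by-side reading followed by an illustration.

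**Reading**

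1. 2.3.1 and 4.5 require a test rating and a diagnosis rating for both notes.
2. 3.4 makes the Note B review depend on an answer about treatment plans.
3. 3.2 describes treatment as medications, care instructions and referrals. A change confined to tests or diagnoses need not count as a treatment difference.
4. In the 3.1 model, a patient with one rated note contributes nothing to the coefficient on assistance, because the patient effect absorbs the single value.
5. The only coding rule for stopped pairs covers the better-plan indicator.

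**Illustration**

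Let g be the share of pairs stopped by the question, d_o the mean within-patient change in a rating among reviewed pairs, and d_c the mean change among stopped pairs.

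- Effect in all patients: (1 − g)·d_o + g·d_c
- Stopped pairs dropped: d_o, an error of g·(d_o − d_c)
- Note A carried over: (1 − g)·d_o, an error of −g·d_c

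The planned size of about 500 patients comes from SAP 2.1 and serves only to scale the counts. The values of g, d_o and d_c are assumptions. Take d_o = 0.20.

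| g | Complete pairs of 500 | All patients, d_c = 0 | d_c = 0.05 | d_c = 0.10 | d_c = 0.20 | Dropped | Carried over |
|---|---|---|---|---|---|---|---|
| 0.2 | 400 | 0.160 | 0.170 | 0.180 | 0.200 | 0.200 | 0.160 |
| 0.4 | 300 | 0.120 | 0.140 | 0.160 | 0.200 | 0.200 | 0.120 |
| 0.6 | 200 | 0.080 | 0.110 | 0.140 | 0.200 | 0.200 | 0.080 |

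One cell in full, for g = 0.4 and d_c = 0.10: the effect in all patients is 0.6 × 0.20 + 0.4 × 0.10 = 0.12 + 0.04 = 0.16. Dropping gives 0.20, which is 0.04 too large. Carrying over gives 0.6 × 0.20 = 0.12, which is 0.04 too small.

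Carrying over is right only if stopped pairs do not change on average (d_c = 0). Dropping is right only if they change as much as reviewed pairs (d_c = d_o). Over this grid either error reaches at most 0.6 × 0.20 = 0.12.

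**The case against.** **The survey itself is not shown.** The stopping rule stands in a section that defines the better-plan indicator, so the review it mentions may be only the treatment and harm part. Section 2.3.1 speaks of ratings for each note, and 3.2 says its treatment question is put for Note B as well, without mentioning a condition. This stands as a limit. A reader might infer that Note B ratings have certainly been lost, and the document does not show that. But nothing in 3.4 narrows the word review, so the literal reading is the one a programmer would follow.

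**Many test changes will open the review anyway.** Both CHEW notes hold plans conditional on test results (2.2), and the MO is told to take conditional treatment into account (3.2). An added test often brings a conditional treatment, which is a treatment difference. An unsure answer also lets the review go on. This stands too: it would be wrong to infer that every change in tests or diagnoses goes unrated. What remains is the narrower group in which the MO sees no meaningful treatment difference, conditional treatment included.

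**The size is assumed.** Stopped pairs include those with essentially identical notes, so d_c may be near zero, and carrying over would then be nearly right. The table shows this case. It illustrates the mechanism and does not estimate the bias.

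**Sections 4.1 and 4.4 already cover diagnoses and tests.** They do so in part. Section 4.1 works from the indication attached to each medication, so a diagnosis without a drug is not captured. Most of 4.4 needs a screening result, which the demographic and symptom criteria restrict. Neither records the MO's judgement of usefulness or correctness, so they cannot stand in for 4.5.

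**Conclusion.** The concern holds as a conflict in wording with a consequence for estimation. Followed literally, 3.4 leaves some pairs with test and diagnosis ratings for Note A only, while 4.5 promises effects that need both notes. Dropping these pairs selects on an event that follows the intervention, and carrying Note A over erases real changes.

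The size is unknown, since it depends on how many pairs are stopped and how far their tests and diagnoses differ; the document gives neither. Only the test and diagnosis items of secondary outcome 4.5 are touched by this gap. A reader might extend it to the primary outcomes, but those rest on treatment errors, harm ratings and screening results, not on these items. The conclusion assumes that the question governs the whole Note B review. If it governs only the treatment and harm items, a clarification in 3.4 is all that is needed.

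**What to change.** 1. **Say what the question governs.** State in 3.4 whether it applies to the test and diagnosis items. If it does not, the remaining steps fall away.
2. **Remaining patients.** Ask the Note B test and diagnosis items whatever the answer to the treatment-plan question. The SAP update is dated 29 April 2025 and the proposed end is 30 May, so this was still open when the update was written. Report results separately for the periods before and after the change.
3. **Patients already rated.** Carry Note A's test (or diagnosis) rating to Note B only where the stored EMR test (or diagnosis) fields of the two notes are identical. Otherwise set Note B to missing, report the count, and give lower and upper bounds for the 4.5 effect. For an item coded 0 or 1, setting every missing Note B value to each extreme in turn gives bounds whose width equals the share of pairs set to missing.
4. **Ungated check.** Compare Note A ratings across patients by assisted status, as 5.1 already does for raw scores, using ratings given before Note B was seen. Use only data from after the note-order randomization was corrected (5.4). This is less precise than the within-patient comparison but does not depend on the question.
5. **Sections 4.1 and 4.4.** Present them as supporting evidence only, in the patients and items they cover.

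The cost is a small change to the survey skip logic, a few MO minutes per stopped patient, a field comparison in code and a paragraph of SAP text. The drawback is two collection periods for the same items, which also has to be kept in mind for the time trends in 5.3.

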4.6 Average and Distribution of DALY lost

We use our DALY measure of harm indirectly in several primary outcomes (probability of error and severe error, which note is the better note). As a secondary outcome, we will measure the effect of LLM assistance on average DALY (this is not our primary outcome because we are concerned about power being limited due to a few outliers).

Additionally, we will show the full distribution of DALY ratings for the assisted and unassisted notes.

4.7 3rd Party MD Review of CHEW notes and MO notes

We will reassess our primary outcomes using the MD DALY ratings and subjective harm measures (section 2.5).

4.8 MO Review Only for Subset Approved by MDs

On the one hand, the reviewing MOs have the best information about the patient, but on the other, they may also make medical errors. Therefore we will also consider replicating our primary outcomes looking only at patients for whom MDs do not identify a serious error in the diagnosis or treatment proposed in the “final” MO note (see section 2.5). We will only drop patients for this secondary outcome if at least two MDs agree on the error identified in the MO’s note.

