2.2 Patient EMR data

All patient data is saved in the EMR. At various points, this data is collated into SOAP notes (structured text files describing subjective and objective signs and symptoms, the provider's assessment (diagnosis), and the treatment plan).

The SOAP notes that are saved are:

- “Unassisted” SOAP note created on initial patient consultation and submitted to LLM: contains care plan conditional on results of requested medical tests, randomly labeled SOAP A or B
- “Assisted” SOAP note created after LLM feedback was received: conditional care plan, randomly labeled B or A
- Conditional MO SOAP note: conditional care plan, created by MO prior to receiving laboratory test results
- Patient discharge SOAP note: patient care plan created by MO after receiving laboratory test results and communicated to patient
- Final MO SOAP note: patient care plan created after reviewing study medical tests (malaria, anemia, UTI).

In addition, we have the values of individual EMR fields that make up these SOAP notes, e.g. test results, diagnoses, prescriptions, etc., including patient demographics and vital signs.

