2.5 MD Panel

A panel of three Medical Doctors (MDs) will review the patient data (CHEW notes, MO notes, and LLM feedback).

Flagging MO error. In a first step, they will review the MO notes only and record whether there is any error in the diagnosis or treatment proposed in the conditional note or in the final note. If an error is identified the MDs will rate the error by severity to distinguish medical mistakes from differences in opinion about a patient who is not present.

SOAP note rating. Next, the MDs will carry out an independent evaluation of the assisted and unassisted SOAP notes as described in the sections “Types of harm incurred” and ”“Measuring Healthy Time Lost” (section 2.3.1 above).

LLM review. Finally, the MDs will also review the LLM feedback and answer the following questions:

“Did the CHEW follow all, some, or none of the LLM recommendations?”

If some or none: "Imagine the CHEW had followed all the recommendations of the LLM. Would the resulting treatment plan be an improvement over their assisted note?" (Yes/no)

If yes: "Please explain."

“Did the LLM make any mistakes?” (Yes/no)

If yes: "Was any aspect of the CHEW's assisted treatment plan worse than the unassisted plan because the CHEW followed the LLM's erroneous recommendation?"

If yes: "Please explain."

3 Primary Outcomes

Our study will have four primary outcomes, each assessing differences between the CHEW's assisted and unassisted note.

1. An indicator for an error in the treatment plan in the SOAP note (with the potential for harm)
2. An indicator for an error in the treatment plan that causes a loss of at least X quality-adjusted life days (where X is the highest benchmark on the appropriate DALY scale so that at least 5% of patients have an error that large in the unassisted SOAP note)
3. An indicator for the better treatment plan

4. Consistency of treatment with the “standard of care” based on our screening tests and medical guidelines.

We describe the construction of each metric in detail below.

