5.2 Data Quality Indicators

Quality of MOs. We will construct objective treatment and testing decision quality indicators for MOs in an analogous way to the measures in sections 3.5 and 4.4 based on the screening test results.

We will also report the share of cases in which MOs update their own treatment plan after reviewing SOAP Note A, SOAP Note B, and the screening test results.

Finally, we will report the assessment of error in the MO’s SOAP note by the MDs.

Quality of DALY measures. We will verify the direction of DALY rating change between Note A and B with the response to the question

All things considered, do you prefer the treatment plan in SOAP Note A or in SOAP Note B?

As a secondary outcome, we will make a scatterplot of QALY loss against whether the MO classifies a patient as mild, moderate, severe, pooling both notes. What we expect to see is that the scope for QALY losses generally occur in the most severe patients.

More generally, we will analyze the response of the DALY ratings of MOs and MDs to subjective and objective indicators of error: indicators for deviations from the MO’s SOAP and types of harm incurred (section 2.3.1) and objective treatment misallocation (3.5).

We will also analyze the agreement between MO and MD DALY ratings relative to the agreement on the various harm measures between the three MDs.

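### The Section 4.8 subset screens only the final MO note, so a patient whose MO plan was wrong at rating and was put right only by the screening results stays in

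*SAP*

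**What the plan says.** Section 4.8 gives its reason plainly: reviewing MOs know the patient best, but "they may also make medical errors". It therefore considers repeating the primary analyses "looking only at patients for whom MDs do not identify a serious error in the diagnosis or treatment proposed in the" MO's last note, labelled final. The bar for exclusion is agreement within the three-doctor panel: "We will only drop patients for this secondary outcome if at least two MDs agree on the error identified in the" MO's note.

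Section 2.2 defines the final MO note as the "patient care plan created after reviewing study medical tests (malaria, anemia, UTI"). It defines the conditional MO note as a "conditional care plan, created by MO prior to receiving laboratory test results".

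Under Section 2.5 the panel looks at both. They are to "record whether there is any error in the diagnosis or treatment proposed in the conditional note or in the final note", and to grade any error by severity. Section 4.8 uses only the final-note part of that record. No other section uses the conditional-note part to define a subset; Section 5.2 reports the panel's assessment of MO error descriptively.

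**The concern.** Three of the four primary outcomes are the MO's own judgement of the CHEW notes. If the MO had the case wrong when rating, a correct CHEW note can be scored as an error and a wrong one as sound. Section 4.8 is the analysis meant to take such patients out.

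To do so, the filter has to inspect the plan the MO held when rating. The final note is a later document, written with information the MO may not have had at that time. A clean final note shows that the MO ended in the right place. It does not show that the ratings were made from there. If the two differ in a meaningful share of patients, agreement between the 4.8 results and the main results would reassure more than it should.

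**Working it through.** The SAP gives no figure here to reproduce. The check is which MO plan the ratings rest on, and whether the filter looks at it.

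**1. Outcomes that depend on the MO's plan.** Any treatment error (3.2), severe error (3.3) and the better-plan indicator (3.4) come from the MO's answers and harm ratings. Treatment misallocation (3.5) rests on test results and treatment guidelines, so the choice of MO note does not touch it.

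**2. The plan used as reference.** Section 2.2 lists three MO notes: conditional, discharge and final. Section 2.3.1 asks for the "expected magnitude of healthy life that would be lost if the CHEW plan were implemented instead of" the MO's plan, and does not say which. Section 3.2 tells the MO to judge against the MO's own diagnosis and to allow for treatments that hinge on test results. The reference is thus not fixed in the text.

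**3. The likely order.** Section 5.2 will report "the share of cases in which MOs update their own treatment plan after reviewing SOAP Note A", then Note B, then the screening results. In that order the final note follows the rating of both CHEW notes. The wording in 3.2 points the same way, since test results seem to be still open at rating. Both are inferences; the SAP sets out no timetable. Section 5.1 describes one revision of a rating: the Note A score may be adjusted once Note B has been seen. No revision after the screening results is described.

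**4. What the 4.8 filter does in each case, if that order holds.**

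| Course of the MO's plan | Final note | 4.8 as written | Standard used at rating |
|---|---|---|---|
| Wrong throughout | Error | Dropped | Wrong |
| Wrong, corrected on reading the CHEW notes | Clean | Kept | May already be the corrected one |
| Wrong, corrected only by the screening results | Clean | Kept | Wrong |
| Sound, error only in the final note | Error | Dropped | Sound |

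The third row is the problem. The fourth costs patients but does not leave a faulty standard in the subset.

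**5. Size.** Let p be the share of patients with a serious error in the conditional MO note and c the share of those corrected by the final note. At most p × c of patients are wrongly kept. The SAP gives neither value. With c = 0.5 assumed:

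- p = 5%: 0.05 × 0.5 = 2.5%
- p = 10%: 0.10 × 0.5 = 5%
- p = 20%: 0.20 × 0.5 = 10%

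These are upper limits for the assumed inputs, because they count row two together with row three.

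**The case against.** The strongest reply is that the SAP never says the CHEW notes are rated against the conditional MO note. Section 2.3.1 speaks only of the MO's plan, and Section 3.2 of the MO's own diagnosis, which can be read as the MO's judgement at that moment. The phrase about conditional treatments may only tell the MO how to read the CHEW's plan. The list in 5.2 is a reporting commitment and not a schedule. This stands as a limit: the order of events is inferred. It does not rescue the filter, which is adequate only if the final note matches the plan used at rating, and the SAP does not say so.

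A second reply also stands. A reader might infer that the subset keeps patients in whom the assisted note itself led the MO to a correction, and that their ratings are faulty. Section 5.1 does not support that. The adjusted ratings are meant to reflect full information and are used in most of the analysis, so a correction prompted by Note A or Note B may already be in them.

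For the same reason, simply replacing the final note by the conditional note is not supported. That would treat the conditional note as the known standard, which it is not, and would ignore errors that appear only in the final note.

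Third, MO error is addressed elsewhere. Section 4.7 reassesses the primary outcomes with the panel's own ratings, and Section 5.2 reports MO quality and how often MOs change their plans. These are separate safeguards and lower the stakes, but they do not change which patients enter the 4.8 subset.

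**Conclusion.** The point holds in a limited form. The filter in 4.8 looks at a note written after the screening results, while the SAP's own wording suggests that the ratings were made before them. Patients whose MO plan was seriously wrong at rating and was corrected only by the screening results would be counted as approved.

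It would go too far to say that 4.8 cannot serve its purpose. It still removes patients whose MO error persisted into the final note. The main estimates and the test-based outcome are unaffected, and 4.8 is a secondary check that the SAP says only that it will consider.

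The conclusion assumes that rating precedes the final note and is not reopened afterwards. The range of up to 2.5% to 10% of patients depends wholly on the assumed error and correction rates and is not an estimate for this study.

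**What to change.** Three changes to the SAP wording:

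- Define the 4.8 subset as patients with no serious error in either the conditional or the final MO note, keeping the rule that at least two of the panel doctors must agree on the error. This covers the third row of the table whether the conditional or the final plan served as the standard.
- Show the final-note-only version beside it as a sensitivity analysis.
- State in 2.3.1 which MO plan is the reference when the CHEW notes are rated, and whether rating is complete before the screening results are seen.

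No new data are needed, because 2.5 already has the panel examine both notes; the flags need to be kept separately by note so that both versions can be run. The price is a somewhat smaller subset. Under the assumptions above, the extra exclusions would be the same 2.5% to 10% of patients, including some whose MO had already corrected the plan when the adjusted rating was given.
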